3.4 Study Endpoints

3.4.1 Primary Study Endpoints

To determine the efficacy of the combination of tDCS and physical training, the following primary outcome measures have been chosen:

- Efficacy measured by comparison between the active and sham conditions by comparing the changes in gait velocity and stride length at baseline and participation end
- Compliance measured by 80% of participants having completed the study sessions

CONFIDENTIAL

This material is the property of the NYU School of Medicine and Langone Medical Center. Do not disclose or use except as authorized in writing by the study sponsor

Interventional Template Version: 28 APR 2017

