This material is the property of the NYU School of Medicine and Langone Medical Center. Do not disclose or use except as authorized in writing by the study sponsor

Interventional Template Version: 28 APR 2017

Session 10)- Optional							
An asterisk next to a measure indicates that it is an optional assessment that may be foregone in the case of limited time and/or limited availability of the ActiGraph Wristwatch device							

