7.1 Statistical Hypotheses

Research hypothesis

There is a significant difference between active and sham groups by comparing primary and secondary outcomes at baseline and end treatment time.

Null hypothesis

There will not be a significant difference between active and sham groups

CONFIDENTIAL

This material is the property of the NYU School of Medicine and Langone Medical Center. Do not disclose or use except as authorized in writing by the study sponsor

Interventional Template Version: 28 APR 2017

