7.2.2 Analysis of the Primary Efficacy Endpoint(s)

Gait speed and Stride length

- Continuous variable (repeated measure)
- The Shapiro-Wilk test will be performed: histograms will be constructed, and measures of central tendency and dispersion will be calculated to test the assumption that distribution is normal
- If normality check will fail a transformation of the data will be done as corrective procedures (transformation will be made according to data distribution)
- Repeated-measures analysis of variance (RM-ANOVA) with tDCS (2 levels: Active and Sham) as the between-independent variable and Time (3 levels: Day 1, Day 10, and After 4-weeks) as the within-independent variable. In the inferential tests statistical significance will be set at 5% and all p-values is two-sided.

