7.3 Sample Size

The sample size is calculated on the primary endpoint gait velocity measured before tDCS treatments at baseline time in a population of individuals affected by MS (0.98 ± 0.23 m/s). According to previous study the variability of changes after tDCS combined with PA is on average around 20% in active group compared with baseline assessment.

To recognize as significant change in gait velocity (alpha level = 0.05), equal to 20% difference between baseline and end of the treatment, a sample size of 19 cases for each arm will provide a power of 80%.

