Interventional Template Version: 28 APR 2017

16 Schedule of Events

Activity	Screening	Baseline	tDCS +activity sessions	Study visit 11/ Treatment End Visit (approx. 3 days after end treatment)	Follow-up visit (Optional) [4 ±1 week post- Study Visit 10]
Study team procedures					
Consent	X				
Medical History	X				
Physical Exam	X				
Height		X			
Weight		X			
Neurological examination	X				
Randomization	X				
tDCS+ PA treatment		X	X	X	
Participant device compliance check				X	
Assessment of perceived exertion (Borg Scale)			X		
Instrumented evaluation of mobility					
i-10MW test		X		X	X
Timed 25-Foot Walk (T25-FW)		X		X	X
i-TUG test		X		X	X
Static Posturography Test	X	X		X	X
EEG assessment (Optional)		X		X	
i-2MW test		X		X	X
i-DPAS (Optional)		X	X	X	X
Questionnaires, Clinical Scale and Cognitive Assessment					
BICAMS		X		X	X
Cogstate Brief Battery		X		X	X
Berg Balance Scale		X		X	X
FSS		X	X	X	X
54-MSQOL		X			X
12-MSWS		X	X	X	X
21- MFIS		X	X	X	X
VAS- F 0-10		X	X	X	X
VAS- P 0-10		X	X	X	
Reported Adverse Events		X	X	X	

CONFIDENTIAL

CONFIDENTIAL

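### The primary RM-ANOVA adds an optional 4-week visit to a baseline-to-end comparison, so as usually fitted it drops participants who have the treatment-end result

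*Combined protocol and SAP*

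**What the plan says.** Three places set the primary question as a two-point comparison:

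- Section 3.4.1 defines efficacy by "comparing the changes in gait velocity and stride length at baseline and participation end".
- Section 7.1 states the hypothesis "by comparing primary and secondary outcomes at baseline and end treatment time".
- Section 7.3 sizes the trial on a change "equal to 20% difference between baseline and end of the treatment".

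Section 7.2.2 then analyses gait speed and stride length by RM-ANOVA with arm as the between factor and "Time (3 levels: Day 1, Day 10, and After 4-weeks) as the within-independent variable". It does not say which effect in that model is the primary test. Section 7 names no analysis set and no statistical method for missing values. The remarks on missing data in sections 8 and 9 concern form completion and data queries.

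The status of the 4-week visit is not consistent. The 4.4 table labels its row "Session 10)- Optional" and puts an asterisk on its gait assessment. The note below that table reads "An asterisk next to a measure indicates that it is an optional assessment that may be foregone in the case of limited time". The section 16 column is headed "Follow-up visit (Optional)". On the other side, section 5.3.5 lists the 4-week i-10MW and marks only the ActiGraph collection as optional. The 4.4 text describes the visit without calling it optional, and section 15 and the Protocol Summary include the 4-week time.

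**The concern.** An assessment that staff may skip should not decide who enters the primary analysis of an outcome measured a month earlier. Classical RM-ANOVA software needs all three values per person. A participant with a baseline and a treatment-end walk who misses the 4-week visit would then be left out of the test of an endpoint already completed. Nothing in section 7 prevents this.

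A second problem remains even with full attendance. The group-by-time test over three visits has two degrees of freedom and asks whether the arms differ in profile anywhere. A significant result need not mean a treatment-end difference, which is what sections 7.1 and 7.3 ask about.

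At stake are usable data, and a primary p-value that answers the stated question.

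**Working it through.** **Inputs from the documents.** Baseline gait velocity 0.98 ± 0.23 m/s, a 20% change, and 19 per arm for 80% power (7.3); two-sided 5% (7.2.2); 80 enrolled, 10% dropout, 72 evaluable (4.5); 1:1 allocation (3.3). The planned change is 0.20 × 0.98 = 0.196 m/s.

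**The plan's own figure.** For a two-arm comparison, n = 2 × (1.96 + 0.842)² × (0.23/0.196)² = 21.6, so 22 per arm (23 with the t distribution). The stated 19 is not reproduced; at 19 per arm power is 72% by t-test. Nothing below depends on 19, because 80 × 0.9 = 72 gives 36 per arm.

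**Assumptions.** The same SD at each visit; equal correlation r between visits, 0.5 or 0.8; all 72 have a treatment-end value; attendance at 4 weeks varied, because the documents give no rate. Section 7.3 describes the 20% as a change that "is on average around 20% in active group compared with baseline assessment". Using 0.196 as an arm difference is therefore itself an assumption, and half of it (0.098) is also shown. The RM-ANOVA test is taken to be group by time.

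**Treatment-end comparison of all 72.**

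- Change score: SD = 0.23 × √(2(1 − 0.5)) = 0.230; SE = 0.230 × √(2/36) = 0.0542; power for 0.196 is 0.946.
- Baseline-adjusted: residual SD = 0.23 × √(1 − 0.5²) = 0.199; SE = 0.199 × √(2/36) = 0.0469; power 0.984. No gain from the EDSS stratum is counted.

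**Three-time group-by-time test on complete cases.** Noncentrality λ = (n/2) × Σ(eₜ − ē)² / (0.23² × (1 − r)), where eₜ is the arm difference at each time and n is per arm; degrees of freedom 2 and 2(2n − 2).

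- Sustained effect (0, d, d): Σ = (2/3)d² = 0.0256; at n = 36, λ = 18 × 0.0256/0.02645 = 17.4.
- Half-faded effect (0, d, d/2): Σ = d²/2 = 0.0192; λ = 13.1.

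Power for 0.196 m/s, r = 0.5:

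| Of 72, with a 4-week value | Three-time, sustained | Three-time, half-faded | Baseline-adjusted, all 72 |
|---|---|---|---|
| 72 | 0.967 | 0.903 | 0.984 |
| 64 | 0.946 | 0.864 | 0.984 |
| 54 | 0.901 | 0.795 | 0.984 |
| 36 | 0.736 | 0.603 | 0.984 |

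For 0.098 m/s with all 72 attending, the baseline-adjusted and three-time (sustained) powers are 0.539 and 0.439 at r = 0.5, and 0.844 and 0.841 at r = 0.8.

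**What the three-time test can detect.** The profiles (0, d, d), (0, d, 0) and (0, 0, d) all give Σ = (2/3)d² and so the same λ. The third has no treatment-end effect at all. The test has the same chance of rejecting in each case and cannot tell them apart.

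Stride length is not calculated because the documents give no SD for it.

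**The case against.** **The 4-week time belongs to the design.** Section 15 and the Protocol Summary list it, and the phrase for the end of participation in 3.4.1 is never defined. If that phrase meant the final visit, the endpoint would sit at 4 weeks. This stands as a reason to define the term and to keep the visit. It does not remove the mismatch: 7.1 and 7.3 both name the end of treatment, and an endpoint at 4 weeks would rest on a visit marked optional.

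**Exclusion is inferred.** No sentence says incomplete cases are dropped. That is correct. The weakness is an unspecified method whose usual implementation has this effect.

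**Attendance may be high.** Inclusion criterion 8 asks for commitment to follow-up visits, and 12.2 pays for the final follow-up visit. Both lower the expected loss. Neither gives a rate or a rule for those who do not come.

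**The third visit can add power.** With full attendance and a sustained effect, the three-time test (0.967) beats the simple two-visit change comparison (0.946), and with 64 complete cases it equals it. So it would be wrong to say that the third time only costs precision. Against a baseline-adjusted comparison the advantage disappears, at both correlations tried.

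**Spare sample size.** For 0.196 m/s with a sustained effect, power stays near 90% even with 54 complete cases. This stands, but both arms exercise, so the arm difference may be smaller than the active-group change.

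**Conclusion.** The point holds as a mismatch between the primary question and the primary model, made worse by the optional visit and the absence of a missing-data method. With full attendance nobody is dropped. What remains is a test that does not isolate the treatment-end difference, with power of about 97% or 90% (sustained or half-faded) against about 98% for the baseline-adjusted comparison. If 54 of 72 attend, the figures are about 90% or 80% against 98%. These rest on SD 0.23, correlation 0.5, 0.196 m/s taken as the arm difference, and assumed attendance.

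Two stronger readings are tempting, and the documents do not support them.

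- A reader might infer that the primary result will be biased, perhaps because 7.4.3 breaks the blind at the end of participation and participants could then decide on the 4-week visit knowing their arm. That visit is not defined and no attendance by arm is given. Neither size nor direction can be stated, and the bias may be zero.
- A reader might infer that people who stop treatment early are never assessed, because only the pregnancy section (6.4.4) describes an assessed end visit. But 4.6.1 refers to a stop-criteria document that was not available, the text between the heading of section 5 and section 5.2 was also not available, and the title of 5.3.6 contemplates an early termination visit. No conclusion is drawn on this.

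**What to change.** In 7.2.2, state that the primary analysis is the difference between arms at the treatment-end visit in gait velocity and in stride length, adjusted for the baseline value and the EDSS randomisation stratum. Fit it by ANCOVA, or by a mixed model using all available visits with the treatment-end difference as the named primary contrast. Keep every randomised participant who has data in the assigned arm. Report the 4-week visit as a secondary time, which agrees with its listing in section 15. Define the end of participation in 3.4.1 as the treatment-end visit, and give the 4-week visit one status across 4.4, 5.3.5 and section 16.

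The cost is wording and a little analysis work, with no added visit or measurement. The mixed model assumes that missing values are predictable from the observed ones, and the plan should say so. ANCOVA uses only those with a treatment-end value.

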7.2.3 Analysis of the Secondary Endpoint(s)

Time Up and Go parameters (temporal parameters: phase duration of Sit-to-Stand, Stand-to-Sit, Mid and End turning; speed rotation; antero-posterior, lateral and vertical acceleration in Sit-to-Stand and Stand-to-Sit phases)

- Continuous variable (repeated measure)
- The Shapiro-Wilk test will be performed: histograms will be constructed, and measures of central tendency and dispersion will be calculated to test the assumption that distribution is normal
- If normality check will fail a transformation of the data will be done as corrective procedures (transformation will be made according to data distribution)
- Repeated-measures analysis of variance (RM-ANOVA) with tDCS (2 levels: Active and Sham) as the between-independent variable and Time (3 levels: Day 1, Day 10, and After 4-weeks) as the within-independent variable. In the inferential tests statistical significance will be set at 5% and all p-values is two-sided.

Static Posturography Parameters or Sway Parameters (velocity of the COP on the AP or ML axes, COP velocity, COP path and COP Area)

- Continuous variable (repeated measure)
- The Shapiro-Wilk test will be performed: histograms will be constructed, and measures of central tendency and dispersion will be calculated to test the assumption that distribution is normal

CONFIDENTIAL

This material is the property of the NYU School of Medicine and Langone Medical Center. Do not disclose or use except as authorized in writing by the study sponsor

Interventional Template Version: 28 APR 2017

- If normality check will fail a transformation of the data will be done as corrective procedures (transformation will be made according to data distribution)
- Repeated-measures analysis of variance (RM-ANOVA) with tDCS (2 levels: Active and Sham) as the between-independent variable and Time (3 levels: Day 1, Day 10, and After 4-weeks) as the within-independent variable. In the inferential tests statistical significance will be set at 5% and all p-values is two-sided.

Questionnaire scores

- Continuous variable (repeated measure)
- The Shapiro-Wilk test will be performed: histograms will be constructed, and measures of central tendency and dispersion will be calculated to test the assumption that distribution is normal
- If normality check will fail a transformation of the data will be done as corrective procedures (transformation will be made according to data distribution)
- Repeated-measures analysis of variance (RM-ANOVA) with tDCS (2 levels: Active and Sham) as the between-independent variable and Time (3 levels: Day 1, Day 10, and After 4-weeks) as the within-independent variable. In the inferential tests statistical significance will be set at 5% and all p-values is two-sided.

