Endpoint	Primary outcome measures: 
Comparison of change in gait velocity and stride length at baseline and participation end between the active and sham conditionsThe number of participants completing the study session (goal: 80% of the participants) Secondary outcome measures: 
% of remote tDCS sessions completedComparison between the active and sham conditions on functional mobility parameters (phase duration of Sit-to-Stand, Stand-to-Sit, Mid and End turning; acceleration and angular velocity) and the Timed Up and Go Task (TUG)Comparison between the active and sham conditions on EEG signals before and after the first and final tDCS sessionComparison between the active and sham conditions on static balance abilityComparisons between the active and sham conditions on Fatigue Severity Scale (FSS), 21-item Modified form of the Fatigue Impact Scale, 12-item Multiple Sclerosis Walking Scale, Multiple Sclerosis Quality of Life-54 (MSQOL-54)
Study Duration	Estimated study start date: June 2018 Estimated study end date:

CONFIDENTIAL

This material is the property of the NYU School of Medicine and Langone Medical Center. Do not disclose or use except as authorized in writing by the study sponsor
Interventional Template Version: 28 APR 2017

[figure not shown]
Participant Duration	Approximately 6 hours to 7 hours total over 9 remote sessions plus a baseline and a follow-up visit.
Duration of IP administration	20 minutes of tDCS in each daily session
Population	Age Eligible for study: 18 years to 70 years Sex Eligible for study: All Condition: Multiple Sclerosis
Study Sites	NYU Langone Health, USA
Number of participants	80 participants
Description of Study Agent/Procedure	
Device: Active tDCS tDCS is a therapeutic treatment that utilizes low amplitude direct currents (<4 mA) to induce changes in cortical excitability. Other Name: Soterix 1x1 tDCS mini-CTDevice: Sham tDCS During a sham session, the device is programmed to ramp up to the desired intensity (target 2.5 mA) and ramp down for the initial 60 seconds, with no current delivery during the session, and then again at the end of the session. These brief periods of stimulation serve to mimic the effects of a true stimulation session.Behavioral: Physical Activity (PA) program consisting of 20 minutes of cycling on an ergonomic cross-trainer.
Reference Therapy	N/A

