3.4.2 Secondary Study Endpoints

- The feasibility of delivering at-home supervised PA paired with tDCS will be assessed using the number of completed sessions at-home. It will be considered as “feasible” when participant complete successfully at least 80% of the total at-home sessions
- Comparisons between the active and sham conditions at baseline and at the end of the study by assessing the changes in gait spatial-temporal parameters (stance, swing and double support phase; cadence; step width) and functional mobility parameters objectively assessed using wearable inertial sensors
- Comparisons between the active and sham conditions at baseline and participation end conditions by assessing the changes in scores of 9-item FSS (physical aspect of fatigue) and 21-item MFIS (physical 9 items, cognitive 10 items, psychosocial 2 items), MSWS-12 (subjective measures of impact for walking ability and related pathology), and MSQOL-54 (36 items for generic health-related quality of life measures and 18 items for MS-specific measures).
- Comparisons between the active and sham conditions at baseline and participation end conditions by assessing the changes in scores of VAS- F₀₋₁₀ (to assess the perceived general fatigue)
- Review of experiences of minor adverse events and pain ratings. In particular, participants will have to report and rate any adverse events. Pain ratings will be measured, using a VAS- P₀₋₁₀ (rating 1 for minimal to 10 for most severe), before and after each session (any experience of pain or other adverse event above an intensity rating of 7 will result in study discontinuation)
- Comparisons between the active and sham conditions at pre and post tDCS-PA session by assessing the changes in the performance of the cognitive tests and EEG signal changes during the time of testing
- Comparisons between the active and sham conditions at baseline and participation end conditions by monitoring the changes in level of daily physical activity and amount of sleep as measured by ActiGraph
- Comparisons between the active and sham conditions at baseline and participation end conditions by monitoring the changes in sway parameters as objectively measured by the instrumented Posturography test and by monitoring changes in total score Berg Balance Scale.
- Change in processing speed between baseline and immediately after the treatment end to assess improvement in cognitive function as indirect effect of aerobic PA.

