Static posturography will be performed according to a standardized procedure as follows:

Each participant will be asked to stand barefoot on the force platform, in upright static condition, double-leg stance, and with arms resting at their sides. The position of the feet on the force-platform is standardized, their feet will be placed on two 30°-oriented footprints (inter-malleolar distance 8 cm) drawn on a paper sheet placed on the force platform. Stance conditions are tested with open eyes (OE) and closed eyes (CE). Each test will be performed 2-3 times based on the ability of each participant and lasts around 30 seconds. The closed eyes static posturography will be an optional assessment depending on the level of impairment of the participant.

Device: Wii Balance Board (Nintendo) paired via Bluetooth device with a PC. It was previously validated for healthy controls and pwMS (Park and Lee, 2014, Pau et al., 2015, Pau et al., 2017).

- **Timed 25-Foot Walk (T25-FW):** it is a clinical tool that evaluates participants for quantitative mobility and leg function performance test in a timed, 25 foot walk. The scoring for the Timed 25-Foot Walk is the average of two trials.

T25-FW procedure: the patient is directed to walk 25 feet quickly and safely as possible. Participant can use the assistive devices while doing this task.

- **Cognitive Assessment**

Brief International Cognitive Assessment in MS (BICAMS) (Benedict et al., 2016): this battery includes tests of mental processing speed and memory. Specifically, it includes the Brief Visuospatial Memory Test (BVMT), Symbol Digit Modality Test (SDMT), and Rey Auditory Verbal Learning Test (RVLT).

Cogstate Brief Battery (Maruff et al., 2009): brief, computer-administered cognitive test battery that requires approximately 10 minutes for administration and consists of four cognitive tasks that measure psychomotor function, attention, working memory and memory.

CONFIDENTIAL

- **Balance Clinical Scale**

Berg Balance Scale (Berg et al., 2005): this scale objectively determine a patient's ability (or inability) to safely balance during a series of predetermined tasks. It is a 14 item list with each item consisting of a five-point ordinal scale ranging from 0 to 4, with 0 indicating the lowest level of function and 4 the highest level of function and takes approximately 20 minutes to complete.

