5.3.4 Treatment End visit (within 3 days after session 10)

- Gait assessment with instrumented 10-meter walk (i-10MW), functional mobility assessment with instrumented Time Up and GO (i-TUG), Timed 25-Foot Walk (T25-FW), instrumented 2 minute walk (i-2MW) test, balance assessment with static posturography test, administration of Berg Balance Scale, and administration of questionnaires (9-item FSS, 21-item MFIS, MSWS-12, 54-MSQOL, and VAS- F 0-10)
- Cognitive assessment using BICAMS and CogState brief battery

5.3.5 Final Study Visit (within 4 ± 1 weeks from the end of treatment i.e. Session 10)

- Gait assessment with instrumented 10-meter walk (i-10MW), functional mobility with instrumented Time Up and GO (i-TUG), and balance assessment with static posturography test, administration of Berg Balance Scale, Timed 25-Foot Walk (T25-FW)
- Administration of questionnaires (9-item FSS, 21-item MFIS, MSWS-12, 54-MSQOL, and VAS- F 0-10)
- Record participant's adherence to treatment program
- Cognitive assessment using BICAMS and CogState brief battery
- Collect the ActiGraph device (Optional)

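### Section 7.2.3 tests about 20 to 29 secondary scores, each at two-sided 5% with no hierarchy, adjustment or supportive label, so the chance of a false positive among them is well above 5%

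*Combined protocol and SAP*

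**What the plan says.** Section 7.2.3 has three blocks of secondary outcomes: TUG, static posturography and questionnaires. Each block has the same model, a group (active, sham) by time (Day 1, Day 10, 4 weeks) repeated-measures ANOVA, and the same rule: "In the inferential tests statistical significance will be set at 5% and all p-values is two-sided".

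- The TUG block lists "phase duration of Sit-to-Stand, Stand-to-Sit, Mid and End turning; speed rotation; antero-posterior, lateral and vertical acceleration in Sit-to-Stand and Stand-to-Sit phases".
- The posturography block lists "velocity of the COP on the AP or ML axes, COP velocity, COP path and COP Area". Section 5.2.1 adds that "Stance conditions are tested with open eyes (OE) and closed eyes (CE"), with the closed-eyes condition optional.
- The questionnaire block names no instrument. Section 5.3.4 shows what is collected: "administration of questionnaires (9-item FSS, 21-item MFIS, MSWS-12, 54-MSQOL, and VAS- F 0-10"). Section 3.4.2 divides one of these into subscales: "21-item MFIS (physical 9 items, cognitive 10 items, psychosocial 2 items").

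Section 7.1 states a single research hypothesis: "There is a significant difference between active and sham groups by comparing primary and secondary outcomes at baseline and end treatment time".

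The Endpoint row of the Protocol Summary lists the TUG phase durations, acceleration and angular velocity, and then a further item: "and the Timed Up and Go Task (TUG").

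Section 7 contains no multiplicity adjustment, order of testing, key secondary endpoint or statement that secondary p-values are supportive, and none appears elsewhere in the document.

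**The concern.** When many scores are each tested at 5% and none is marked as the one that counts, the chance that at least one falls below 0.05 without any treatment effect is much larger than 5%. The wording of 7.1 adds to this: because secondary outcomes share the primary hypothesis, a reader could take one significant secondary score as support for it.

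At stake are the conclusions on functional mobility, balance and fatigue, which could rest on whichever of 20 or more scores happened to reach significance. The TUG list adds a smaller problem. The TUG as a whole is named in the synopsis, but the analysis section spells out only its parts, so 11 component results could be reported without the overall one. The primary analysis of gait speed and stride length is not affected.

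**Working it through.** The plan states neither a number of secondary tests nor a familywise error rate, so there is no figure of its own to reproduce.

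**Step 1: count the scores.**

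- TUG (7.2.3): 4 phase durations + 1 rotation speed + 3 acceleration axes × 2 phases = 11.
- Sway (7.2.3): 5 if AP velocity, ML velocity, COP velocity, path and area are separate; 4 if COP velocity only repeats the axis velocities. If eyes-open and eyes-closed are analysed separately, which 7.2.3 does not say, this becomes 8 or 10.
- Questionnaires (5.3.4, 3.4.2): 5 instruments (FSS, MFIS, MSWS-12, MSQOL-54, VAS-F), or 8 if the MFIS total is tested together with its 3 subscales.

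Smallest reading: 11 + 4 + 5 = 20. Largest: 11 + 10 + 8 = 29. A middle reading is 11 + 5 + 8 = 24.

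**Step 2: independent tests, all null hypotheses true, one test per score.** Chance of at least one p<0.05 = 1 − 0.95^m; expected false positives = 0.05 × m.

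| m | Chance of at least one | Expected number |
|---|---|---|
| 11 (TUG only) | 1 − 0.95^11 = 43.1% | 0.55 |
| 20 | 1 − 0.95^20 = 64.2% | 1.00 |
| 24 | 1 − 0.95^24 = 70.8% | 1.20 |
| 29 | 1 − 0.95^29 = 77.4% | 1.45 |

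**Step 3: correlated tests.** The scores are certainly correlated, but the documents give no correlations. The values below are assumptions. Two-sided z tests were simulated (100,000 draws) in blocks of 11 TUG, 5 sway and 8 questionnaire scores, with one correlation within a block and another between blocks.

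| Within / between | 24 scores, at least one p<0.05 |
|---|---|
| 0.3 / 0.1 | 64.7% |
| 0.5 / 0.2 | 55.6% |
| 0.7 / 0.2 | 45.2% |
| 0.9 / 0.2 | 30.5% |
| 0.9 / 0.9 | 16.2% |

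With 21 scores (11, 5 and 5) the figures at 0.5/0.2, 0.7/0.2 and 0.9/0.9 are 51.8%, 42.4% and 15.9%, so the result depends much more on the correlation than on the exact count.

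**Step 4: more than one test per score.** Section 7.2.3 does not say which ANOVA effect is the test. If the group effect and the group-by-time interaction are both read for each of 24 scores, the chance is 91.5% if independent (1 − 0.95^48), 80.4% at 0.5/0.2 and 70.3% at 0.7/0.2 (simulated, 50,000 draws).

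Section 3.4.2 also names secondary endpoints that 7.2.3 does not itemise (other gait parameters, Berg Balance Scale, cognition, EEG, ActiGraph). They are left out of the count and would raise it.

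**The case against.** The protocol calls itself a pilot and separates primary, secondary and exploratory endpoints. Unadjusted secondary tests are common in such a study and do little harm if they are read as supportive. Section 7.1 states no success rule, so it does not say that one significant secondary score would establish anything. These points have weight and are why a change of wording is enough. They do not remove the concern. The plan nowhere applies the supportive label, the synopsis says the study is to test efficacy, and the exploratory tier (3.4.3, 7.2.6) holds only the MRI correlation.

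Correlation is the stronger technical objection. Many of these scores come from the same trial: three acceleration axes belong to one movement, and COP path over a stance of about 30 seconds is close to COP velocity restated. High correlation within a domain is plausible, and it lowers the risk materially.

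A reader might go further than the documents allow in three ways:

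- **That exactly 24 tests are planned.** The document gives no count. Reaching 24 requires choices about sway, eye conditions or MFIS scoring that 7.2.3 does not make.
- **That a chance significant result is likely.** In the one-test-per-score simulation this holds at low to moderate correlation, but the chance is below one half at 0.7/0.2 and above.
- **That the synopsis promises total TUG time and the plan leaves it without a test.** The synopsis names the task and does not mention total time. Total time is a fair inference, because the components are listed separately, but it remains an inference. The general approach in 7.2.1 would also supply a method for an overall TUG score. What stands is that 7.2.3 does not list one.

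**Conclusion.** The concern holds in this form: as written, the secondary analyses carry a false-positive risk well above 5%, and the plan does nothing to control or label it. If no treatment effect exists, the chance of at least one p<0.05 is 64% to 77% for 20 to 29 independent tests. For 24 correlated tests it is about 56% at 0.5/0.2, 45% at 0.7/0.2 and 16% if every correlation is 0.9. Even that last figure is about three times the nominal level. The independent figures are an upper guide for one test per score, and reading two effects per score gives higher values.

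These results assume that all null hypotheses are true and rest on assumed correlations; the range of counts reflects what 7.2.3 leaves open. The missing overall TUG result is a gap between the synopsis and the analysis list.

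**What to change.** 1. In 7.1, limit the research hypothesis to the primary outcome.
2. In 7.2.3, state that secondary scores are supportive and will be reported as between-group differences in change with 95% CI and no significance claim.
3. Add the overall TUG result to the 7.2.3 list and say which score it is, so that the list agrees with the synopsis.
4. If the sponsor wants confirmatory secondary claims, name one score per domain in advance, with the contrast and time point (for example, active versus sham change from baseline to treatment end), and test those with Holm at 5%. The documents do not favour one score over another within a domain, so the choice is the sponsor's. Holm used this way controls error within the named secondary scores only, not jointly with the primary outcome.

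The cost is wording in two sections, with no new assessments. The downside is that fewer secondary results can be called significant.
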